#### **4.8.4 Missing Data**

Analyses of efficacy and safety will be based on available cases, without imputation for missing values.

#### **4.8.5 Interim Analyses**

No formal schedule of interim analyses is planned. Reports of adverse events from this extension study may be reviewed and summarized periodically while the study is ongoing to ensure the safety of subjects.

### **4.9 DATA QUALITY ASSURANCE**

Accurate, consistent, and reliable data will be ensured through the use of standard practices and procedures.

## **5. ASSESSMENT OF SAFETY**

The safety of ranibizumab will be assessed through the collection and analysis of rates of primary safety outcomes.

### **5.1 ADVERSE EVENTS**

*All adverse events occurring from Day 0 through Month 12 or Early Withdrawal will be documented and assessed by the principal investigator.* Subjects discontinuing early from the study should return for an early termination evaluation and will be contacted 7 days after their last injection or study visit to elicit for occurrence of adverse events (serious and nonserious).

For this protocol, an AE is any “on study” untoward medical occurrence (e.g., sign, symptom, disease, syndrome, intercurrent illness) that occurs in a study subject, regardless of the suspected cause. “On study” refers to Day 0 through the last study visit.

Unchanged, chronic conditions are NOT AEs and will not be recorded. An exacerbation or worsening of a chronic condition should be recorded as an AE.

Both serious and nonserious AEs should be graded on a three-point scale (mild, moderate, severe) and reported in detail in the subjects clinic record.

The suggested definitions are as follows:

Mild: Discomfort noticed but no disruption of normal daily activity

Moderate: Discomfort sufficient to reduce or affect normal daily activity

Severe: Incapacitating with inability to work or perform normal daily activity

Using the following criteria, the investigator will also assess whether there is a reasonable possibility that study drug caused or contributed to the AE.

- Yes (possibly or probably)

There is a clinically plausible time sequence between onset of the AE and study drug administration; and/or

There is a biologically plausible mechanism for study drug causing or contributing to the AE; and

- No

The AE may or may not be attributed to concurrent/underlying illness, other drugs, or procedures.

A clinically plausible temporal sequence is inconsistent with the onset of the AE and study drug administration; and/or

A causal relationship is considered biologically implausible.

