## **2. OBJECTIVES**

*This Phase I study will investigate the safety and tolerability of intravitreally administered Ranibizumab in three initial monthly doses of 2.0 mg followed by a 9 month period of criteria-based, as-needed retreatment and 12 month off drug safety follow up in subjects with exudative polypoidal choroidal vasculopathy (PCV) for a total of 24 months.*

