### **2.1 Primary Objective**

To investigate the safety and tolerability of 3 initial intravitreally administered injections of 2.0 mg Ranibizumab with a 9 month PRN treatment period and 12 month off drug safety follow up.

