### **2.0 mg Ranibizumab cohort**

Twenty eyes will be treated; PCV eyes may be treatment naïve or received previous PCV therapy greater than 30 days prior to enrollment. A maximum of 10 eyes that completed 24 month enrollment in our study evaluating 0.3 mg or 0.5mg Ranibizumab may be included. *Eyes will be treated with 3 monthly doses of 2.0 mg ranibizumab followed by 2.0mg ranibizumab on a PRN dosing regimen for 9 months.*

*In the year 2 off drug treatment period subjects will be contacted via telephone interview for review of adverse events at month 18 and month 24.*

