**Month(s) 18 & 24**

Telephone Interview to assess for adverse events. Subjects will not be eligible to receive 2.0mg Ranbizumab. Alternate treatments are at the investigators discretion during the off drug observational period.

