#### **Patient Accrual-**

Subject Accrual per Month:1

Date of First Subject Enrolled: November 1, 2010

Date of Last Subject Enrolled: July 1, 2012

Date of Last Subject Completing Study: July 1, 2013

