### **3.2 RATIONALE FOR STUDY DESIGN**

The route (intravitreal injections) and 2.0 mg dose employed is currently evaluated in the HARBOR clinical trial evaluating 2.0 mg Ranibizumab in neovascular AMD. The three consecutive monthly injections will be followed by observation or therapy at the discretion of the investigator. Given the variable course of PCV and unknown response to 2.0 mg Ranibizumab, this regimen will allow the opportunity to evaluate Ranibizumab's safety and potential therapeutic efficacy, as well as to give the patient the opportunity to continue Ranibizumab or switch to an alternative non-anti-VEGF therapy. The 1 year duration of the study is of sufficient duration to determine significant safety issues as well as determine potential efficacy. The possible inclusion of patients completing month 24 follow up after receiving 0.3mg or 0.5 mg doses in our previous study, will determine significant safety issues as well as determine potential efficacy of the 2.0mg dose for this population, as well.

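### Adverse-event follow-up runs to Month 24 in the objectives and schedule, but to Month 12 in Section 5.1, and the stated completion date gives the last subject only 12 months

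*Combined protocol and SAP*

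**What the plan says.** **Text that carries follow-up to Month 24**

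- Section 2 sets out a "12 month off drug safety follow up in subjects with exudative polypoidal choroidal vasculopathy (PCV) for a total of 24 months".
- Section 2.1 puts the off-drug year inside the primary objective: a "9 month PRN treatment period and 12 month off drug safety follow up".
- Section 3.1, in the cohort description, says "subjects will be contacted via telephone interview for review of adverse events at month 18 and month 24". The visit list for those months repeats it: "Telephone Interview to assess for adverse events".
- The flowchart in Appendix A marks the adverse-event and concomitant-medication review in the Month 18 and 24 column.
- Section 5.2 treats worsening of a baseline condition after treatment as a recordable event.

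**Text that points to Month 12**

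- Section 5.1: "All adverse events occurring from Day 0 through Month 12 or Early Withdrawal will be documented and assessed by the principal investigator".
- Section 3.1, accrual: last enrolment on July 1, 2012, and "Date of Last Subject Completing Study: July 1, 2013".
- Section 3.2: "The 1 year duration of the study is of sufficient duration to determine significant safety issues".

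**Text that does not settle it**

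- Section 5.1 also defines an adverse event as one occurring on study, a term that "refers to Day 0 through the last study visit". It does not say whether a telephone interview is a visit.
- The primary outcome (3.3.1) and the safety analysis (4.8.2) give no time window. Section 5.5.4 follows reported events until resolution or the end of participation and names no month.

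**The concern.** The incidence and severity of adverse events is the primary outcome, and safety over the 12 off-drug months is part of the primary objective. Section 5.1 is where site staff will look to decide what to record, grade and assess for causality. If they apply its Month 12 sentence, events reported at the Month 18 and 24 calls need not enter the record. If they close the study on the stated date, some of those calls never take place. In either case the off-drug part of the objective is answered incompletely, and it is unclear how many subjects, and how much time, stand behind any second-year event rate.

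There is also an effect during the trial. Section 3.4 withholds injections pending review after any death, or after thromboembolic events in two or more patients. On the stated dates the first subject passes Month 12 in November 2011, eight months before the last enrolment, so off-drug events in early subjects bear on that review while others are still being treated.

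**Working it through.** **Inputs**

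- 20 subjects (Section 4.1.1).
- Accrual of 1 per month; first enrolment November 1, 2010; last enrolment July 1, 2012; last completion July 1, 2013 (Section 3.1).
- 24 months per subject, of which the last 12 are off drug (Sections 2 and 2.1).
- Off-drug contacts at Months 18 and 24 only (Section 3.1, Appendix A).

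**Step 1: the plan's own accrual figure.** November 1, 2010 to July 1, 2012 is 20 months. At 1 per month this gives 20 subjects, so the stated accrual agrees with the sample size.

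**Step 2: the completion date.** July 1, 2012 to July 1, 2013 is 12 months, against 24 required: a shortfall of 12. First enrolment to stated completion is 32 months. With 24 months for a subject enrolled on July 1, 2012, completion is July 1, 2014, which is 32 + 12 = 44 months from first enrolment. The first figure fits the 2–3 years in Section 4.8.1; the second does not.

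**Step 3: what Section 5.1 covers.** Planned off-drug time is 20 × 12 = 240 subject-months. A window closing at Month 12 covers 0 of 240.

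**Step 4: what the stated completion date would allow.** The plan gives no individual enrolment dates, so I assume roughly monthly enrolment, no dropout, and contacts falling exactly on July 1, 2013 counted as made. For a subject with f months of follow-up on that date, off-drug time elapsed is min(f, 24) − 12. Off-drug time covered by a contact is 12 if f ≥ 24, 6 if 18 ≤ f < 24, and otherwise 0.

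| Enrolment pattern | f (months) | Reach M24 | Reach M18 | Off-drug months elapsed | Contacts made, of 40 | Off-drug months covered by a contact |
|---|---|---|---|---|---|---|
| Monthly, Nov 2010–Jun 2012 | 32 down to 13 | 9 | 15 | 9×12 + (11+…+1) = 174 | 9+15 = 24 | 9×12 + 6×6 = 144 |
| Monthly, Dec 2010–Jul 2012 | 31 down to 12 | 8 | 14 | 8×12 + (11+…+1) = 162 | 8+14 = 22 | 8×12 + 6×6 = 132 |
| Evenly spaced, Nov 1, 2010–Jul 1, 2012 | 32 down to 12 | 8 | 14 | 165.5 | 22 | 132 |

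Enrolling monthly from November 2010 to July 2012 with any one intermediate month skipped stays inside these ranges.

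As proportions:

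- Off-drug time elapsed: 162/240 = 67.5% to 174/240 = 72.5%.
- Contacts made: 22/40 = 55% to 24/40 = 60%.
- Off-drug time covered by a contact: 132/240 = 55% to 144/240 = 60%.

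All 20 subjects reach Month 12 under every pattern.

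**Step 5: can the on-study definition reconcile the texts?** If a telephone interview is a study visit, the definition reaches Month 24 and conflicts with the Month 12 sentence in the same section. If it is not, Section 5.1 ends at Month 12 and conflicts with Sections 2, 2.1 and 3.1 and Appendix A. Neither reading removes the contradiction.

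**The case against.** The strongest reply is that Section 5.1 does not say later events are to be ignored. It states what will be done through Month 12; its on-study definition and its grading instruction carry no Month 12 limit. Other sections narrow the gap: 5.2 records post-treatment worsening, Appendix A schedules the review at Months 18 and 24, expedited reporting under 5.5.5 runs from the investigator's knowledge of the event, and 3.4 has any death reviewed. So zero of 240 is the result of one sentence, not of the whole protocol. That is fair, and the figure should be read that way. But these provisions cover classes of event or say when to ask. They do not establish that every off-drug event is documented and assessed, which is what the primary outcome needs.

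Second, the July 2013 date is a forecast, and nothing says contacts or analysis stop then. That also stands: the figures in Step 4 are conditional on the date being applied, and it may simply not have been updated. It is still wrong for a 24-month study, and it agrees with the Month 12 sentence and the one-year wording in 3.2. That wording could mean the treatment year, and the 2–3 years in 4.8.1 is feasibility language, so both are weaker support.

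Third, Section 4.8.3 gives the denominator as patients enrolled, and no separate second-year rates are planned. However, Section 4.8.4 uses available cases, so a second year recorded for only some subjects would still be hard to interpret.

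Finally, this is a small descriptive pilot, and no power or error rate depends on the point. It is also true that no eye examination, acuity or vital-sign check is scheduled after Month 12, so correcting the text will not by itself make off-drug safety fully observed. Neither fact removes a conflict about the period over which the primary objective is assessed.

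**Conclusion.** The contradiction is real and sits in current text. The objectives, the design section and the flowchart require adverse-event follow-up to Month 24; the Section 5.1 recording sentence and the accrual dates stop at 12 months per subject; and nothing says which prevails. The 12-month shortfall in the completion date follows from the stated dates alone. The number of subjects and contacts lost is conditional: if July 1, 2013 were applied as a stop, 8–9 of 20 subjects would reach Month 24 and 22–24 of 40 off-drug contacts would be made, assuming about one enrolment a month and no dropout. If the Month 12 sentence were applied literally, off-drug events would fall outside the documentation requirement altogether. Because this affects the primary objective, I rate it a must-fix.

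**What to change.** - **Section 5.1:** extend the documentation and assessment window to the Month 24 telephone contact or early withdrawal, and state that the Month 18 and 24 contacts count as on study.
- **Section 3.1:** set the last-subject completion date 24 months after last enrolment, which is July 1, 2014 on the stated accrual.
- **Section 3.2:** align the one-year duration with 24 months, or say that it means the treatment year.
- **Section 4.8.1:** replace the 2–3 year estimate with about 44 months from first enrolment.
- **Optional:** tabulate events collected in clinic (Day 0 to Month 12) separately from those reported by telephone (Month 12 to 24), since they are ascertained differently.

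The cost is wording and dates. The stated study duration becomes 12 months longer, but the Month 18 and 24 contacts are already scheduled, so no new contacts are needed.

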### **3.3 OUTCOME MEASURES**

#### **3.3.1 Primary Outcome Measure**

The primary outcome measure for safety and tolerability is the following:

Incidence and severity of ocular and systemic adverse events. Examples include 30 letter loss, major subretinal hemorrhage, involving 75% or more of clinical macula (arcade to arcade), disease-related vitreous hemorrhage, injection-related endophthalmitis, retinal detachment, vitreous hemorrhage, *study drug/procedure* -

related uveitis, incidence and severity of other adverse events, as identified by physical examination, subject reporting, and changes in vital signs.

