## **5.5.4 Type And Duration Of Follow-Up After Adverse Events**

All reported AEs should be followed until resolution or until the subject's participation in the study ends. Subjects who have an ongoing study drug-related SAE at study completion or at discontinuation from the study will be followed by the investigator or his or her designee until the event is resolved or determined to be irreversible, chronic, or stable by the investigator.

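### Relatedness is a single Yes/No for study drug with overlapping criteria, and no rule assigns the cause-labelled events in Section 3.3.1 to the injection or the disease

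*Combined protocol and SAP*

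**What the plan says.** **Recording.** For every AE, Section 5.1 has the investigator judge "whether there is a reasonable possibility that study drug caused or contributed to the AE". The answer is Yes or No.

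- Yes rests on timing, "There is a clinically plausible time sequence between onset of the AE and study drug administration; and/or", or on mechanism, "There is a biologically plausible mechanism for study drug causing or contributing to the AE; and".
- No rests on timing, "A clinically plausible temporal sequence is inconsistent with the onset of the AE and study drug administration; and/or", or on mechanism, "A causal relationship is considered biologically implausible".

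The criteria mention illness, other drugs and procedures only to say that the AE may or may not be due to them. That is true of any AE.

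**Outcome.** The primary outcome in Section 3.3.1 covers all ocular and systemic AEs. Its examples include "disease-related vitreous hemorrhage, injection-related endophthalmitis, retinal detachment, vitreous hemorrhage" and uveitis related to study drug or procedure. Section 3.4 also groups serious events by source, but only by naming examples.

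**Use of the answer.** Section 5.5.4 extends follow-up beyond the study for one class of event: "Subjects who have an ongoing study drug-related SAE at study completion or at discontinuation from the study will be followed". The expedited-reporting text in Section 5.5.5 and the MedWatch guidance in Section 5.5.5.1 also tie relatedness to the drug or product.

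**The concern.** Safety is the only primary outcome of this uncontrolled study, so no comparator arm can help separate the effects of drug, injection and disease. Attribution therefore rests on what the investigator records for each event.

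There are two separate defects:

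1. **Overlap.** The Yes and No criteria are not complementary, so two careful assessors can follow the text and give opposite answers for the same AE.
2. **Missing attribution.** The recorded item concerns study drug only, while some outcome events are named by injection or disease. Even a clean drug item would not supply that information.

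At stake are the consistency of any drug-related count and the ability to report the cause-labelled events as Section 3.3.1 names them.

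**Working it through.** The plan states no figure on this point, so there is none to reproduce.

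**Step 1: the criteria.** Let T mean plausible timing and M mean plausible mechanism. As written, Yes = T or M, and No = (not T) or (not M).

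| T | M | Yes met | No met |
|---|---|---|---|
| yes | yes | yes | no |
| yes | no | yes | yes |
| no | yes | yes | yes |
| no | no | no | yes |

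Two of the four combinations satisfy both answers. The line order of this list may have been disturbed in conversion from PDF, but the result does not depend on it. The remark about other causes is always true, so attaching it to either answer changes nothing.

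**Step 2: cause labels against recorded items.**

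| Label in Section 3.3.1 | Planned item or rule |
|---|---|
| Disease-related vitreous hemorrhage | none for disease |
| Injection-related endophthalmitis and the events listed after it | none for the injection |
| Study drug/procedure-related uveitis | drug item only |

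Vitreous hemorrhage is the clearest case. Section 3.3.1 gives it once as disease-related and again in the run that begins with injection-related endophthalmitis. Section 3.4 also lists it twice, once among events of the injection and once among serious ocular events. The event term alone therefore cannot place it. The event is realistic: Section 1.3 reports two mild vitreous hemorrhages in the group's earlier 20-eye study.

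**Step 3: effect of one reclassified event.** Section 4.8.3 reports rates as a percentage of patients enrolled, and n = 20. Moving one subject between categories changes each rate by 1/20 = 5 percentage points. Exact (Clopper-Pearson) 95% intervals:

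- 0/20 = 0%: 0 to 16.8%
- 1/20 = 5%: 0.1 to 24.9%
- 2/20 = 10%: 1.2 to 31.7%

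**Step 4: expected serious procedure events.** Appendix A shows injections at Day 0, Months 1 and 2, and possibly Months 3 to 11: 3 + 9 = 12 per eye, and 20 × 12 = 240. Sections 4.3.2 and 4.4 extend optional treatment to Month 12: 3 + 10 = 13 per eye, and 20 × 13 = 260. These passages need reconciling, so both totals are carried. Section 1.5 cites serious procedure-related events in under 0.1% of injections:

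- 240 × 0.001 = 0.24
- 260 × 0.001 = 0.26

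The expected number is therefore below about 0.24 to 0.26, even if every optional injection is given.

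**The case against.** **The primary outcome survives.** A reader might infer that the primary outcome cannot be derived. The documents do not support that. The outcome is all AEs, Section 5.1 defines an AE whatever its suspected cause, and the cause-labelled events are introduced as examples. Overall incidence and severity can be tabulated in full.

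**Some causes can be inferred.** Endophthalmitis could often be linked to the injection from the event term and injection dates. Section 5.1 asks for detail in the clinic record, and Section 5.5.1 asks for secondary events to be identified by primary cause. The uveitis label joins drug and procedure, so it needs no split between them. This stands, but it gives no rule for vitreous hemorrhage. From Month 3, Section 4.4 also permits laser, photodynamic therapy (PDT) and steroids, including intravitreal steroids, as competing causes.

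**An injection-caused event is not necessarily No.** A reader might infer that such an event must be marked No and so falls outside Section 5.5.4. Under the written criteria, plausible timing is enough for Yes, so the answer is ambiguous. Any gap in follow-up is conditional and narrow. Section 5.5.4 follows all reported AEs until resolution or the end of participation. Section 3.1 schedules AE calls at Months 18 and 24, and early leavers have a termination evaluation.

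**Common reactions carry no cause label.** Conjunctival hemorrhage, eye pain, floaters and raised intraocular pressure are not named by cause in Section 3.3.1, so no stated category is lost for them. That is right. They are affected only through the overlapping drug item.

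**Scale.** This is a single-site study of 20 subjects with AEs assessed by the principal investigator, which limits disagreement between assessors. It does not make the criteria determinate. The AE form is not in the documents and may hold more than Section 5.1 describes.

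**Conclusion.** The concern holds in a limited form. Section 5.1 allows both answers in 2 of 4 timing/mechanism combinations, and no planned variable or rule assigns an event to the injection procedure or to PCV. The cause-labelled events in Section 3.3.1 and any drug-related count therefore cannot be classified consistently. Overall AE incidence and severity are unaffected.

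The size is modest in events but visible in rates: 5 percentage points per reclassified subject. Fewer than about 0.24 to 0.26 serious procedure events are expected, assuming the rate cited in Section 1.5 carries over to this dose and population. The practical effect falls on vitreous hemorrhage and on drug-related counts for common injection reactions. Monthly injections make plausible timing frequent, so mixed cases are likely, though the documents give no basis for estimating how many.

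The conclusion assumes that Section 5.1 describes everything planned for recording causality. It is worth correcting because safety is the sole primary outcome and attribution is best recorded when the event occurs.

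**What to change.** 1. For each ocular AE, record separate relatedness items for study drug, injection procedure, underlying PCV and other permitted therapy (laser, PDT, steroids).
2. Make Yes and No mutually exclusive. If Yes keeps the and/or, No should require that both timing and mechanism fail. If Yes requires both, No should cover the rest. State the choice before data are collected.
3. Tabulate the cause-labelled events in Section 3.3.1 by these items, including both entries for vitreous hemorrhage.
4. Reconcile the drug-only wording of Section 5.5.4 with the drug/procedure label in Section 3.3.1.

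**Cost.** A few AE form fields and short edits to Sections 5.1 and 5.5.4. The number of events counted as related may rise. If plausible timing alone is enough for Yes, the rise could be noticeable under monthly dosing, and more unexpected serious events could fall under the expedited-reporting rules of Section 5.5.5. Requiring both criteria for Yes would avoid that, but would put the mixed cases under No.
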